4 STUDY DESIGN

4.1 OVERALL DESIGN

This is a multi-site, two-arm, non-blinded randomized controlled non-inferiority trial that includes 6 months of participation from enrollment to final follow-up.

Hypothesis: We hypothesize that the EPP IUD expulsion rate at 6 months postpartum will be lower than the reported expulsion rate for IPP IUDs (24%) and non-inferior at a 6% margin to the expulsion rate for interval postpartum IUDs (previously reported at 3-5%).

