4.2 SCIENTIFIC RATIONALE FOR STUDY DESIGN

Traditionally, IUDs are placed at 6-8 weeks postpartum, therefore the standard of care will serve as the control condition. We are using a 6% non-inferiority assuming a 4% expulsions rate in the interval group according to prior research. This difference is presumed to be clinically meaningful.

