9.2 SAMPLE SIZE DETERMINATION

We hypothesize that EPP IUD expulsion will be non-inferior to interval insertion. We propose that greater than or equal to a 6% difference in expulsion at 6 months postpartum between the two arms is clinically meaningful (6% non-inferiority margin). Therefore, we estimate that 404 women will be needed [202 in each arm] to achieve an 80% power to detect a difference of 6% in expulsion at 6 months at a significance level of .05 (two-sided alpha), assuming a 15% loss to follow up and that 5% of IUDs would not be placed after randomization (due to patient preference or new medical contraindication or inability to place the IUDs) and assuming a 4% expulsion rate in the interval group. We estimate that enrolling 404 patients allows us to achieve an 80% power to detect a difference of 6% or more between groups with a 1-sided type 1 error of 0.25%.

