9.4 STATISTICAL ANALYSES

9.4.1 GENERAL APPROACH

9.4.2 ANALYSIS OF THE PRIMARY EFFICACY ENDPOINT(S)

Our primary outcome, the proportion of women with complete IUD expulsion at 6 months after delivery in the two groups, will be compared in the modified intention-to-treat (MITT) cohort using the Wald test. Women who change their mind about receiving the IUD after randomization, choose to receive the IUD after 6 months, or women who choose not to participate in the study any time after randomization, will be excluded from analysis for the MITT analysis. In addition, we will present a per-protocol analysis. The per-protocol analysis will include women who received their treatment according to the timeframe in which they were randomized. For the early IUD insertion group, per-protocol analysis will include women with documented receipt of the IUD insertion between 14 and 28 days postpartum. For the interval IUD insertion group, the per-protocol analysis will include only women with documented receipt of a postpartum IUD between 42-56 days postpartum. In both the MITT and per-protocol analyses IUD expulsion rates will be compared using the 2-sided test of noninferiority. If the CI for the risk difference does not cross the prespecified 6% margin, noninferiority will be confirmed.

We will consider imputing missing data. However, if one group had no or few expulsion outcomes the model may not converge.

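### Section 9.2 claims 80% power for the same 404 women at two type I error rates that differ tenfold, and section 9.4.2 gives no confidence level for the interval that decides non-inferiority

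*Combined protocol and SAP*

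**What the plan says.** Section 9.2 makes two power statements about the same 404 women (202 per arm), the same 6% difference and the same 80% power. The first sets the test "at a significance level of .05 (two-sided alpha"). It allows for attrition by "assuming a 15% loss to follow up and that 5% of IUDs would not be placed after randomization", with 4% expulsion in the interval arm. The second, which closes the section, claims "an 80% power to detect a difference of 6% or more between groups with a 1-sided type 1 error of 0.25"%.

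Section 9.4.2 says the primary outcome "will be compared in the modified intention-to-treat (MITT) cohort using the Wald test" and that "IUD expulsion rates will be compared using the 2-sided test of noninferiority". Its decision rule is: "If the CI for the risk difference does not cross the prespecified 6% margin, noninferiority will be confirmed". It gives neither a confidence level nor an alpha, and no confidence level appears elsewhere in the supplied text.

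The interval-arm rate is repeated in section 4.2 ("assuming a 4% expulsions rate in the interval group according to prior research"). Section 4.1 hypothesises that early placement is "non-inferior at a 6% margin to the expulsion rate for interval postpartum IUDs (previously reported at 3-5"%). No numeric expulsion rate for the early postpartum (EPP) arm is given for the power calculation.

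**The concern.** For a non-inferiority bound, two-sided 5% is one-sided 2.5%. The closing sentence of 9.2 gives one-sided 0.25%, and 2.5 / 0.25 = 10. Power at a fixed sample size falls as alpha falls, so for any single pair of expulsion rates at most one of the two 80% statements can be right.

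The alpha also sets the interval used in the decision rule: 100 − 2 × 2.5 = 95% for the first statement and 100 − 2 × 0.25 = 99.5% for the second. Section 9.4.2 does not choose between them. What is at stake is the primary conclusion, because some results would be non-inferior at one level and not at the other. If the level is settled only after the data are seen, the primary test is no longer prespecified.

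**Working it through.** **Inputs.** From 9.2: margin 0.06; interval rate pC = 0.04; power 80% (z = 0.8416); 202 per arm; 15% loss plus 5% not placed. The EPP rate pE is not stated. I take pE = 0.04 (equal rates, the usual non-inferiority assumption) and then vary it. z is 1.960 at one-sided 2.5% and 2.807 at one-sided 0.25%.

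**1. Reproducing 404.** The unpooled formula matches the Wald test in 9.4.2:

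n per arm = [pC(1−pC) + pE(1−pE)] × (z_alpha + 0.8416)² / (0.06 − (pE − pC))²

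- One-sided 2.5%: 0.0768 × 7.849 / 0.0036 = 167.4, so 168. Then 168 × 1.20 = 201.6, so 202 per arm, **404 in total**, as stated.
- One-sided 0.25%: 0.0768 × 13.313 / 0.0036 = 284.0, so 285. The total is 684 (× 1.20), 706 (/ 0.8075) or 714 (/ 0.80).

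**2. Does 404 identify the alpha?** Not by itself.

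- A Farrington-Manning formula (variance restricted to a difference of 0.06, 4% in both arms) gives n = 161.0 at one-sided 5%. Then 161.0 / 0.80 = 201.3, so 202 per arm, again 404 (400 to 406 across rounding and retention by division; 390 with × 1.20).
- The same formula gives n = 206.6 (total 498 to 518) at 2.5% and n = 357.5 (total 860 to 896) at 0.25%.
- The unpooled formula at 0.25% with pE = 2.7% gives n = 161.56. Then 161.56 / 0.80 = 201.9, so 202 per arm, also 404.

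With 4% in both arms, neither formula gives 404 at 0.25%.

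**3. Power with 404 enrolled.** Evaluable per arm: 202 × 0.80 = 161.6, or 202 × 0.85 × 0.95 = 163.1.

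Power = Φ( (0.06 − (pE − pC)) / SE − z_alpha ), with SE = √{[pC(1−pC) + pE(1−pE)] / n}

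At 4% in both arms and n = 161.6, SE = 0.0218 and 0.06 / SE = 2.752. Power is Φ(0.792) = 78.6% at 2.5% and Φ(−0.055) = 47.8% at 0.25%. At n = 163.1 it is 79.0% and 48.3%. With the interval rate at 4% and n = 161.6:

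| True EPP rate | Power, one-sided 2.5% | Power, one-sided 0.25% |
|---|---|---|
| 2% | 98.8% | 92.2% |
| 2.7% | 95.4% | 80.0% |
| 3% | 92.9% | 73.2% |
| 4% | 78.6% | 47.8% |
| 5% | 58.3% | 26.2% |

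Exact binomial enumeration of the Wald rule at 162 per arm, 4% in both arms, gives 79.1% and 51.8%. At 0.25%, power reaches 80% only if the EPP rate is at or below 2.4%, 2.7% or 3.0% for interval rates of 3%, 4% or 5% (exact: 2.8% at interval 4%).

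**4. Effect on the verdict.** Take 7/162 EPP and 6/162 interval expulsions. The difference is 0.0062 and SE is 0.0218.

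- 95% upper limit: 0.0062 + 1.960 × 0.0218 = 0.0489, below 6%: non-inferior.
- 99.5% upper limit: 0.0062 + 2.807 × 0.0218 = 0.0674, above 6%: not shown.

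The exact probability that the 95% interval passes and the 99.5% interval fails (162 per arm, interval 4%) is 14%, 18%, 27% and 29% for true EPP rates of 2.7%, 3%, 4% and 5%.

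**The case against.** The strongest reply is that this is a misplaced decimal point. The .05 two-sided level in 9.2 and the two-sided test in 9.4.2 lead by ordinary convention to a 95% interval, and nothing in the plan mentions a 99.5% interval. The alternative routes to 404 are also weak evidence. Farrington-Manning at one-sided 5% matches neither stated alpha and is not the Wald test, and the 2.7% EPP rate is back-solved. Between the two stated alphas, with the Wald variance and equal rates, only 2.5% gives 404. The 79% figure comes from multiplying by 1.20 instead of dividing by 0.80, not from the alpha conflict.

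Much of this stands. A slip for 2.5% is the likeliest explanation, the 99.5% results show only what the second statement means if read literally, and the gap between 79% and 80% is small and separate.

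The reply does not remove the contradiction. The 95% level remains an inference: 9.4.2 does not state it and the last sentence of 9.2 contradicts it. The equal-rates assumption behind the match to 404 is not in the plan either. Section 2.2 reports no complete expulsions in earlier EPP studies and section 2.3.1 expects a risk no higher than standard, so an EPP rate of 2.7% or lower is not excluded. At 2.7%, power at 2.5% would be about 95%, and the first 80% statement would be the wrong one.

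**Conclusion.** The concern holds. Section 9.2 gives two incompatible error rates for one sample size, and the rule for the primary conclusion names no confidence level. Under any single set of expulsion rates, at least one of the two 80% power statements is wrong. With 4% in both arms (the EPP value is an assumption) and about 162 evaluable per arm, the closing sentence overstates power by about 32 percentage points (80% against 48%), while the first statement is right to within about one point. That one-sided 2.5% was meant is a well-supported inference, but the documents do not establish it and the sample size alone does not prove it. The point should be corrected, because it concerns the type I error of the primary test.

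**What to change.** 1. **Section 9.2.** The sponsor should confirm that one-sided 2.5% was intended. If so, replace the 0.25% figure with: one-sided 2.5% (equivalent to two-sided 5%). Keep 404 women.
2. **Section 9.2.** State the assumed EPP expulsion rate and the sample-size formula. If the assumed rate is 4%, the power to state is about 79% with about 162 evaluable per arm.
3. **Section 9.4.2.** State that non-inferiority is declared if the upper limit of the two-sided 95% confidence interval for the risk difference (EPP minus interval) is below 6%.

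The cost is wording in two sections. It needs no extra participants or visits. If the EPP rate is stated as 4%, the quoted power drops from 80% to about 79%.

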9.3 POPULATIONS FOR ANALYSES

The following datasets will be utilized for analysis:

- Intention-to-Treat Analysis Dataset: All participants randomized with known outcomes at the 6 month follow up visit*.
- Modified Intention-to-Treat Analysis Dataset: Participants who received an IUD within 6 months of delivery with known outcomes at the 6 month follow up visit*.
- Per-Protocol Analysis Dataset: Participants who received an IUD within the specified timeframe as designated by their group assignment with known outcomes at the 6 month follow up visit (14-28 days in the early group and 42-56 days in the interval group)*.

*participants known to have an IUD outcome by ultrasonography, pelvic examination, or a contact up to 240 days postpartum will be included.

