8.3.4 TIME PERIOD AND FREQUENCY FOR EVENT ASSESSMENT AND FOLLOW-UP

The occurrence of an adverse event (AE) or serious adverse event (SAE) may come to the attention of study personnel during study visits and interviews of a study participant presenting for medical care, by communication from the participant to the study team, or upon review by a study monitor.

All AEs including local and systemic reactions not meeting the criteria for SAEs will be captured. Information to be collected includes event description, time of onset, clinician's assessment of severity, relationship to study product (assessed only by those with the training and authority to make a diagnosis), and time of resolution/stabilization of the event. All AEs occurring while on study must be documented appropriately regardless of relationship. All AEs will be followed to adequate resolution.

Any medical condition that is present at the time that the participant is screened will be considered as baseline and not reported as an AE. However, if the study participant's condition deteriorates at any time during the study, it will be recorded as an AE. Changes in the severity of an AE will be documented to allow an assessment of the duration of the event at each level of severity to be performed. AEs characterized as intermittent require documentation of onset and duration of each episode.

At each study visit, the investigator will inquire about the occurrence of AE/SAEs since the last visit. Events will be followed for outcome information until resolution or stabilization.

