9.4.3 ANALYSIS OF THE SECONDARY ENDPOINT(S)

Partial IUD expulsion and perforation will be analyzed with the same methods as the primary outcome. IUD discontinuation over the six-month study period will also be analyzed using survival analysis. Data will be censored either (1) at the last date of contact if a participant is lost to follow up or (2) time of IUD removal. The Log-rank test will be used for an unadjusted comparison of the two survival functions. This will be presented graphically using Kaplan-Meier curves.

For other secondary outcomes, normally distributed, continuous variables will be compared using Student's t-tests as appropriate. The Mann-Whitney U test will be used to compare other continuous variables that are not normally distributed. Proportions will be compared using chi-square tests. For small cell sizes, Fisher's exact test will be used as appropriate.

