9.4.4 SAFETY ANALYSES

AEs and SAEs will be recorded by the study team when they become aware. Adverse events leading to premature discontinuation from the study intervention and serious treatment-emergent AEs will be presented in a table.

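### The between-arm perforation comparison omits perforations at attempts after which no IUD is placed and, in MITT, those in women who later withdraw; no safety population is defined for the adverse event table

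*Combined protocol and SAP*

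**What the plan says.** Section 9.3 lists the datasets to be used, and each requires a known outcome:

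- ITT: "All participants randomized with known outcomes at the 6 month follow up visit".
- MITT: "Participants who received an IUD within 6 months of delivery with known outcomes at the 6 month follow up visit".
- Per-protocol: "Participants who received an IUD within the specified timeframe as designated by their group assignment with known outcomes at the 6 month follow up visit".

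A footnote to all three widens the meaning of a known outcome: "participants known to have an IUD outcome by ultrasonography, pelvic examination, or a contact up to 240 days postpartum will be included". No safety set is listed.

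Section 9.4.2 runs the primary comparison in MITT and adds a per-protocol analysis. It also excludes from MITT women who change their mind about the IUD and women who leave the study at any time after randomisation. Section 9.4.3 then states: "Partial IUD expulsion and perforation will be analyzed with the same methods as the primary outcome". Section 3 lists perforation as a tertiary/exploratory objective and defines it by imaging: the device is absent from the uterus on ultrasound but seen on pelvic x-ray at 6 months.

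On safety data, 8.3.4 says: "All AEs occurring while on study must be documented appropriately regardless of relationship". Section 8.2 includes IUD perforation among the serious adverse events that count towards convening the DSMB. Section 9.4.4 says that "serious treatment-emergent AEs will be presented in a table", together with adverse events leading to discontinuation, and names no analysis set. Section 9.2 allows for 15% loss to follow-up and assumes that "5% of IUDs would not be placed after randomization (due to patient preference or new medical contraindication or inability to place the IUDs".

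**The concern.** Perforation is one of the two device harms that 2.3.1 singles out, and the exposure that causes it is the insertion attempt. Restricting the comparison to women in whom a device was placed, who stayed in the study and whose outcome is known, selects on events after randomisation that the harm itself can bring about. A difficult insertion can end without a device; a woman who has been harmed may withdraw.

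The selection need not be equal between arms. Section 2.2 attributes a small increase in perforation risk to interval insertion, and 2.3.1 suggests that the thicker early uterine wall may protect. If insertion risk depends on timing, and timing is what is randomised, failed attempts may also differ by arm. The documents do not show in which direction.

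With few perforations expected, a rule that leaves out recorded ones can alter the reported rates, and readers will use those rates to counsel women about early insertion.

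**Working it through.** **1. The plan's own figure.** Inputs from 9.2: 4% expulsion in both arms, 6-point margin, 80% power, two-sided 0.05 (one-sided 0.025).

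n per arm = 2 × 0.04 × 0.96 × (1.960 + 0.842)² / 0.06², which is just over 167, so 168.

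Inflated by the 15% and 5% allowances added together: 168 × 1.20 = 201.6, so 202 per arm and 404 in total. This matches the plan. The plan itself therefore expects about a fifth of women to be outside the analysed set.

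**2. Women expected outside MITT.**

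- Lost to follow-up: 404 × 0.15 = 60.6, about 61.
- No IUD placed: 404 × 0.05 = 20.2, about 20.
- Allowances added: 404 × 0.80 = 323 in MITT, 81 outside (20%).
- Allowances compounded: 404 × 0.85 × 0.95 = 326 in MITT, 78 outside (19%).

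The 20 or so without an IUD combine preference, new contraindication and inability to place. Only the last clearly involves an attempt, and its share is not given: 0 to about 20.

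**3. Where a recorded perforation goes under the plan as written.**

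| Perforation | MITT comparison | Per-protocol comparison | Section 3 definition | 9.4.4 table |
|---|---|---|---|---|
| At an attempt, no IUD ever placed | Out: no IUD received | Out: no IUD received | Cannot be met if no device is left to see | Not excluded |
| IUD placed, woman later withdraws | Out under 9.4.2 | Depends on whether an outcome is known | Needs the 6-month imaging | Not excluded |
| Documented, woman then lost without withdrawing | Unclear: the footnote may admit her | Unclear, same reason | Needs the 6-month imaging | Not excluded |
| Found and resolved early, woman followed to 6 months | Woman in | Woman in, if placed in her window | Missed if the device is no longer there | Not excluded |

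The first row concerns women who never receive an IUD. A woman whose first attempt fails but who has a device placed within 6 months of delivery can enter MITT. ITT does not require a device, but 9.4.2 does not use it for the primary outcome, so 9.4.3 does not bring it in for perforation.

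**4. What the denominator does.** Four serious events, purely as an illustration, are 4/404 = 0.99% of all randomised women and 4/326 = 1.23% of MITT. These lie on either side of the 1% level in 8.2, whose denominator is also not stated. With no events in an arm, the exact one-sided 95% upper bound, 1 − 0.05^(1/n), is 1.83% for n = 162 (about half of 323) and 1.47% for n = 202. A set based on attempts would lie between these.

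**5. Effect on the 6% margin.** Suppose two perforations are restored to the early arm and none to the other, with 162 women per arm. The difference is 2/162 = 1.23%, with standard error √(0.0123 × 0.9877 / 162) = 0.87%. The Wald upper limit is 1.23% + 1.96 × 0.87% = 2.9%, inside 6%.

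**The case against.** A reader might infer that harms at failed insertions, and in women later lost, are excluded from the trial's safety results altogether. The documents do not say so. Section 9.4.4 is tied to no set in 9.3 and carries no 6-month condition, 8.3.4 requires every event to be documented, and 8.2 counts perforation as serious. Such an event can appear in the table and count towards DSMB review. What is missing there is a stated population and denominator.

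Four further points on the other side stand:

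- Pelvic infection is not among the outcomes that 9.4.3 assigns to the primary methods. No set is named for it, so it cannot be said to be restricted to MITT.
- The footnote gives no earliest date for the contact. A perforation documented before a woman is lost may count as a known IUD outcome. The clear exclusions are the woman who never receives an IUD and, in MITT, the woman who withdraws.
- The 78 to 81 women are not a count of exposed women. They include women who declined, who developed a contraindication, or who were lost before any attempt.
- One or two restored events would not overturn a non-inferiority statement at 6%, as step 5 shows, and 9.4.4 is descriptive.

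It can also be objected that a wider population alone would backfire. Under the section 3 definition, a failed attempt that leaves no device cannot be an event, so adding those women would only dilute the rate. That is correct, and the definition must therefore change with the population. None of this answers the narrower point that 9.4.2, 9.3 and 9.4.3 together remove some recorded perforations from the comparison by rule.

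**Conclusion.** The point holds for the perforation comparison and, as an omission, for the safety table. By the plan's stated rules, a perforation at an attempt after which no IUD is placed is outside both comparisons, and one in a woman who withdraws is outside MITT. The 6-month imaging definition also misses a perforation that leaves no device or is resolved earlier. The 9.4.4 table has no stated denominator.

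About 19-20% of randomised women are expected outside MITT, assuming the 9.2 allowances are borne out. That is the size of the excluded group, not of the bias. The documents give neither a perforation rate at failed attempts nor any link between harm and loss, so the number of harms dropped cannot be estimated. Nothing here bears on the expulsion endpoint or the sample size. It should be corrected before analysis because it affects a named harm and the remedy is cheap.

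**What to change.** 1. Add a safety set to 9.3: all randomised women with an attempted IUD insertion, whether or not a device was placed, the woman later withdrew, or her 6-month outcome is known. Use events recorded up to last contact.
2. Use it for the perforation comparison in 9.4.3, for pelvic infection, and as the denominator of the 9.4.4 table. Report by arm, with failed attempts shown.
3. For this perforation analysis, count any perforation documented from the insertion attempt to 6 months, not only those that meet the section 3 imaging definition.
4. State the earliest contact that counts under the 9.3 footnote.
5. Keep MITT and per-protocol for the expulsion endpoints.

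The cost is SAP wording and new table denominators, with no change to sample size or visits. Event recording is already required by 8.3.4. The content of the provider questionnaires in 8.1 is not shown, so confirm that attempts without placement are recorded. Some women will have less than 6 months of follow-up; reporting follow-up time by arm deals with that.
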